4. SUMMARY OF STUDY DESIGN

Changed: approximately 150 patients

Changed to: up to 200 patients

Added to list of Day 1 activities: and the C-SSRS.

Changed: PK blood samples will be obtained in the morning before dosing at all return visits except Months 4.5, 7.5 and 10.5.

Changed to: PK blood samples will be obtained in the morning before dosing at return visits on Months 15 and 18.

5.1 STUDY POPULATION

Changed: Between 100 and 150 patients will be enrolled

Changed to: Up to 200 patients will be enrolled

5.3 Exclusion Criteria

Changed 29, 30, 31, 32, 33: Prior to randomization

Changed to: Prior to enrollment

Changed 41: Loss of significant volume of blood (>450 mL) within 4 weeks prior to the study

Changed to: Loss of significant volume of blood (>450 mL) within 4 weeks prior to enrollment

Changed 42: COVID-19 infection within 3 months

Changed to: COVID-19 infection within 3 months of screening

7.2.1 Screening Visit 1 (days -29 to 0)

Added: Confirmation that the patient is either fully vaccinated for the COVID-19 virus at least 2 weeks prior to first dose of simufilam, or a positive serology test for the COVID-19 virus with no current symptoms

7.2.4 Follow-up Visits on Months 1, 3, and 9, 13, 15 and 21

Changed: Within 30 min prior to dosing, the following assessments will be conducted:

• Blood sample collection for PK assessment (for C_{min})

Changed to: Within 30 min prior to dosing, the following assessments will be conducted:

• Blood sample collection for PK assessment (for C_{min} – Month 15 only)

Changed: Cheek swab for genetic testing Month 15 Visit only

Changed to: Saliva collection for genetic testing Month 15 Visit only

7.2.5 Follow-up Visit on Month 2

Deleted: Blood sample collection for PK assessment (for C_{min})

7.2.6 Follow-up Visits on Months 4.5, 7.5, and 10.5

Changed: Patients will return to clinic at any time of day

Changed to: Patients will return to clinic at any time of day. The visit may be conducted by telemedicine, based on the judgement of the Investigator

7.2.7 Follow-up Visit on Month 6 and 18

Changed: Blood sample collection for PK assessment (for C_{min})

Changed to: Blood sample collection for PK assessment (for C_{min} – Month 18 only)

Moved from *After Dose* to *Within 30 min prior to dosing*: Plasma sample collection (from 8 mL whole blood) for SavaDx and other plasma biomarkers.

7.2.8 Follow-up Visit on Month 12 and 24

Added for clarity: Month 12 morning dose in the clinic will be from Open-Label Period 1 bottle. Month 12 evening dose will be from the Randomized Period 2 bottle.

Deleted: Blood sample collection for PK assessment (for C_{min})

Moved from *After Dose* to *Within 30 min prior to dosing*: Plasma sample collection (from 8 mL whole blood) for SavaDx and other plasma biomarkers.

7.3.2 Preparation of Plasma Samples for Lymphocyte and Plasma Biomarker Determination

Added: These patients with prior samples shipped as whole blood will continue to have samples shipped as whole blood only through Month 12. Samples at Months 15, 18, 21 and 24 will be spun to plasma.

7.3.3 Preparation of Plasma Samples for Pharmacokinetic Determination

Changed: At each blood collection for PK (pre-dose samples for C_{min} at all visits except Months 4.5, 7.5 and 10.5),

Changed to: At each blood collection for PK (pre-dose samples for C_{min} at Months 15 and 18 only),

7.3.5 Collection of Cheek Swab Saliva Samples for Genetic Testing

Entire section changed from: Cheek swab saliva samples will be collected only at Month 15. Patients will refrain from eating or drinking 1 h prior to saliva collection. Each patient will be instructed to place a standard $2" \times 2"$ piece of cotton gauze in the buccal region of their cheek for 3 min. The saliva-saturated cotton spit wad will be removed, rolled to fit a collection tube, and stored at -20°C until instructed to ship by the Sponsor.

Changed to: Saliva samples will be collected only at Month 15. Patients will refrain from eating or drinking 1 h prior to saliva collection. Each patient will be instructed to spit into a saliva collection tube. The saliva will be stored at -20°C until instructed to ship by the Sponsor.

8. EARLY DISCONTINUATION

Changed: Patients who discontinue will not be replaced.

Changed to: Patients who discontinue may be replaced at Sponsor discretion.

9.5 SERIOUS ADVERSE EVENTS REPORTING

Added: or notification via email through the EDC system

10.2 PHARMACOKINETIC ANALYSIS

Changed: The only plasma PK parameters to be collected from this study are the C_{min} values from blood samples taken prior to dosing on Months 1, 2, 3 and 9, as well as the sample on Month 6 or 12 collected just after the CSF draw (taken only if undergoing a CSF draw).

Changed to: The only plasma PK parameters to be collected from this study are the C_{min} values from blood samples taken prior to dosing at Months 15 and 18.

10.5 PHARMACOKINETIC ANALYSIS

Changed: Between 100 and 150 patients

Changed to: Up to 200 patients

1. LIST OF ABBREVIATIONS

| α7nAChR | α 7 nicotinic acetylcholine receptor |
|--------------------|--|
| $A\beta_{42}$ | anyloid beta ₁₋₄₂ |
| AChEI | acetylcholinesterase inhibitor |
| AD | Alzheimer's disease |
| ADAS-Cog11 | |
| ADAS-Cog11 ADME | Alzheimer's Disease Assessment Scale cognitive subscale 11 |
| ANDI | absorption, distribution, metabolism, excretion |
| | Alzheimer's Disease Neuroimaging Initiative adverse event |
| AE ALP | |
| ALP | alkaline phosphatase |
| ANOVA | alanine transaminase |
| | analysis of variance |
| AST | aspartate transaminase |
| AUC | area under the curve |
| BUN | blood urea nitrogen |
| CFR | Code of Federal Regulations |
| C _{min} | minimum plasma concentration |
| C _{max} | maximum plasma concentration |
| CSF | cerebrospinal fluid |
| CSI | Cassava Sciences, Inc. |
| C-SSRS | Columbia-Suicide Severity Rating Scale |
| DSMB | Data Safety Monitoring Board |
| ECG | electrocardiogram |
| eCRF | electronic case report form |
| EDTA | ethylenediaminetetraacetic acid |
| ELISA | enzyme-linked immunosorbent assay |
| FDA | Federal Drug Association |
| FIH | first in human |
| FLNA | filamin A |
| GCP | good clinical practice |
| GDS | geriatric depression scale |
| GGT | gamma glutamyl transpeptidase |
| GLP | good laboratory practice |
| HBsAg | hepatitis B surface antigen |
| HCV | hepatitis C virus |
| HIV | human immunodeficiency virus |
| hERG | human ether-a-go-go-related gene |
| IB | Investigator's Brochure |
| ICF | Informed consent form |
| ICH | International Council on Harmonization of Technical |
| | Requirements for Registration of Pharmaceuticals for Human |
| | Use |
| IR | insulin receptor |
| IRB | Institutional Review Board |
| | |

| LDH | lactose dehydrogenase |
|------------------|--|
| LOQ | limit of quantitation |
| MI | myocardial infarction |
| MMSE | Mini-Mental State Examination |
| MRI | magnetic resonance imaging |
| mTOR | mammalian target of rapamycin |
| NMDAR | N-methyl D-aspartate receptor |
| NOAEL | no observable adverse effect level |
| NOEL | no observable effect level |
| NfL | neurofilament light chain |
| NPI | neuropsychiatric inventory |
| OTC | over-the-counter |
| РК | pharmacokinetics |
| PTI-125 | small molecule drug candidate to treat AD |
| PTI-125Dx | blood-based diagnostic/biomarker candidate |
| RBC | red blood cell |
| SAD | single ascending dose |
| SAE | serious adverse event |
| SOP | standard operating procedure |
| TLR4 | toll-like receptor 4 |
| T _{max} | time to C _{max} |
| ULN | upper limit of normal |
| WBC | white blood cell |
| YKL40 | chitinase-like protein 1, a secreted glycoprotein associated with inflammation and tissue remodeling |

2. INTRODUCTION

2.1. MECHANISM OF ACTION

Cassava Sciences, Inc. is developing simufilam, a novel drug candidate designed to treat and slow the progression of Alzheimer's disease (AD). Simufilam binds with femtomolar affinity to an altered conformation of filamin A (FLNA) that is induced by beta amyloid₁- $_{42}$ (A β_{42}), present in AD brain and critical to the toxicity of A β_{42} .¹⁻³ Simufilam binding reverses the altered FLNA conformation and restores FLNA's native shape, preventing two toxic signaling cascades of $A\beta_{42}$. $A\beta_{42}$, in monomer or small oligomer form, hijacks the α 7-nicotinic acetylcholine receptor (α 7nAChR) and signals via this receptor to hyperphosphorylate tau. This signaling requires the recruitment of altered FLNA to this receptor. Second, altered FLNA also links to toll-like receptor 4 (TLR4) to allow A_{β42} to persistently activate this receptor. Normal FLNA does not associate with either α 7nAChR or TLR4. In addition to disrupting the normal functions of α 7nAChR and tau protein, $A\beta_{42}$'s toxic signaling to hyperphosphorylate tau leads to the signature tangles and plaques in AD brain. In two AD mouse models and in postmortem human AD brain tissue, simufilam restored function of three receptors that are impaired in AD: the α 7nAChR, the N-methyl-D-aspartate receptor (NMDAR), and the insulin receptor (IR).^{2,3} Simufilam also improved synaptic plasticity and reduced tau hyperphosphorylation, amyloid deposits, neurofibrillary tangles and inflammatory cytokine release.^{2,3} We therefore expect simufilam both to improve cognition and to slow AD progression. Both mouse models used a dose of 20 mg/kg/day (equivalent to $60 \text{ mg/m}^2/\text{day}$).

2.2. SAFETY PHARMACOLOGY AND TOXICOLOGY

A robust nonclinical ADME, safety pharmacology, and general and genetic toxicology program has been conducted with simufilam. In vitro metabolic profiling showed minimal metabolism across several species including humans. Simufilam was rapidly absorbed and eliminated in in vivo studies in rat and dog with nearly 100% oral bioavailability, a 2.67-h half-life in dog, dose-proportional PK and no accumulation. Safety pharmacology studies showed no adverse effects on gross behavioral and physiological parameters in the Irwin test of CNS toxicity in rats, no adverse effects on respiratory rate, tidal volume or minute volume in the rat respiratory test, and no adverse effects on arterial blood pressure, heart rate and ECG parameters in the dog cardiovascular study. The in vitro hERG test for cardiotoxicity also indicated no adverse effect. A full battery of genotoxicity studies was conducted (in vitro bacterial Ames, in vitro chromosomal aberration, and in vivo rat micronucleus test) and were all negative. An in vitro specificity screen showed no significant activation or inhibition of a panel of 68 receptors, channels and transporters.

Simufilam was tested in single dose and repeat dose oral toxicity studies in rats and dogs. A 6-month repeat dose oral toxicity study in rat (PTI-125-NC-049) used the same doses as a 28-day study (50, 500 and 1000 mg/kg/day), which found 500 mg/kg/day to be the no observable adverse effect level (NOAEL). In the 6-month study, the toxicological response was characterized by decreased body weights and adverse structural and functional alterations in the liver of 500 and 1000 mg/kg animals, including increased weight, hepatocellular hypertrophy and vacuolation, single/multiple basophilic/ eosinophilic/clear cell focus, hepatocellular degeneration, pigmentation, and oval cell hyperplasia. The presence of bile pigment was consistent with cholestasis. These findings correlated with changes to the clinical chemistry profile, including increased ALP and total/direct bilirubin. Over the 1-month recovery period, there was complete recovery of the hepatocellular degeneration and partial recovery of hepatocellular hypertrophy. The NOAEL from this 6-month study was 50 mg/kg/day (equivalent to 300 mg/m²). A second ongoing 6-month repeat dose oral toxicity study in rat will more accurately determine the 6-month NOAEL in rat. Doses are vehicle and 125 and 250 mg/kg/day.

In a 9-month toxicity study in dog (PTI-125-NC-050), the no observable effect level (NOEL) of simufilam was 25 mg/kg. The 200 mg/kg (high) dose was decreased to 150 at 1 month due to bodyweight loss thought unsustainable for 9 months. Clinical signs were salivation and a few instances of muscle fasciculations. There were no pathology findings, but the high dose was considered adverse due to two unexplained deaths. The 75 mg/kg/day NOAEL provides 38- and 19-fold safety margins by C_{max} and AUC over the 100 mg b.i.d. dose in patients.

2.3. CLINICAL STUDIES

2.3.1. *A first-in-human Single Ascending Dose clinical trial*

A first-in-human, double-blind, Single Ascending Dose clinical trial was conducted in healthy normal volunteers, age 18-45 with oral dosing solution. Doses were placebo, 50, 100 and 200 mg (equivalent to 31, 62, and 123 mg/m², respectively) administered to three different groups of volunteers. The study showed dose proportional PK, and there were no drug-related adverse events (AEs).

2.3.2. First-in-patient multidose clinical trial in mild-to-moderate AD patients

In a Phase 2a 28-day study, 13 mild-to-moderate AD patients received simufilam 100 mg b.i.d. as oral tablets. Patients were MMSE ≥ 16 and ≤ 24 , age 50-85, with a CSF total tau/A β_{42} ratio ≥ 0.30 . A second CSF sample was collected on Day 28, allowing assessment of change from baseline in biomarkers using commercial ELISA kits. All 8 biomarkers that are elevated in AD were significantly reduced from baseline (**Fig. 1**).⁴ A β_{42} , which is low in AD, was increased slightly but non-significantly. Reduced inflammatory cytokines and YKL-40 indicated reduced neuroinflammation. A reduced neurodegenerative drive was suggested by reductions in neurogranin, neurofilament light

chain, and total tau. The robust reduction in phospho-tau (P-Tau181) confirms the mechanism of action of simufilam. Simufilam was safe and well tolerated in all patients.

[figure not shown]
[figure not shown]

Fig. 1 Phase 2a Mean Change from Baseline to Day 28 in CSF biomarkers (±SEM)

2.3.3. Double-blind placebo-controlled clinical trial in mild-to-moderate AD patients

A Phase 2b randomized, placebo-controlled clinical trial of simufilam 50 or 100 mg tablets or placebo (1:1:1) enrolled 64 mild-to-moderate AD patients with MMSE 16-26. Both 50 and 100 mg doses significantly improved eleven CSF biomarkers of AD pathology, neurodegeneration, neuroinflammation and blood-brain barrier integrity (**Fig. 2**). CSF biomarker analyses were conducted blind to treatment and timepoint by an outside lab, and screening and Day 28 samples for each patient were measured in triplicate in the same ELISA plates. Albumin and immunoglobulin G (IgG) were measured by immunoblotting and quantified by densitometric quantitation. These data suggest disease modification and replicate our Phase 2a results in a well-controlled study.

The secondary endpoints in the Phase 2b trial were two cognitive measures using the Cambridge Neuropsychological Test Automated Battery. Patients were assessed on the Paired Associate Learning (PAL) test, measuring episodic memory, and a test of spatial working memory. The primary outcome measures for each were total errors, with errors imputed for more difficult levels not reached in the PAL test. Simufilam produced encouraging effect sizes (calculated by Hedge's g for group sizes of 20), suggesting cognitive enhancement (**Fig. 3**). Effect sizes versus placebo for the test of episodic memory were 37% and 23% for the 50 and 100 mg groups, respectively, after removing the most and least impaired subjects by baseline score. For spatial working memory, effect sizes were 17% and 46% for these respective dose groups. Cognitive enhancement by simufilam is supported by preclinical data showing improved function of α 7nAChR, NMDAR and insulin receptors and improved synaptic plasticity in 3xTg AD mice and in postmortem human AD brain tissue. In both Phase 2 clinical trials, simufilam was well tolerated and no patients discontinued due to AEs.

[figure not shown]

Fig. 3 Phase 2b Mean Change from Baseline to Day 28 in Total Errors in Memory Test

2.3.4. Open-label safety clinical trial in mild-to-moderate AD patients

We are conducting a 1-year, open-label safety study in mild-to-moderate AD patients. The study was meant to offer open-label drug to participants of our two Phase 2 studies and is also enrolling new patients. In the first 50 patients to reach 6 months, simufilam improved cognition and behavior at 1, 3 and 6 months. ADAS-Cog11 scores improved 1.6 points and NPI scores improved 1.3 points from baseline at 6 months. Mean baseline MMSE was 22.1, and mean ADAS-Cog11 was 15.5 for these 50 patients.

3. STUDY OBJECTIVES

The objectives of this study are to establish 1-year safety and to investigate the effect of simufilam on biomarkers, cognition and neuropsychiatric symptoms during 12-month repeat-dose oral administration in mild-to-moderate AD patients, 50-85 years of age. An objective of the 6-month randomized withdrawal is to determine whether mild-to-moderate AD patients, age 50-85, who have completed a one-year open-label study of 100 mg b.i.d. simufilam and who continue with active dosing will show slower decline on ADAS-Cog11 and the NPI than patients who withdraw from this treatment.

4. SUMMARY OF STUDY DESIGN

The first 12 months is an open-label treatment of simufilam 100 mg b.i.d. for patients who completed prior Phase 2 studies PTI-125-02 and PTI-125-03. New patients are included so that up to 200 patients are enrolled in this study. Month 12 to Month 18 is a randomized withdrawal phase; patients will be randomized to continue taking simufilam 100 mg b.i.d. or matching placebo. Month 18 to Month 24 will be an additional 6 months of open-label simufilam 100 mg b.i.d. Simufilam and placebo will be administered as coated oral tablets. Patients who were enrolled prior to this amendment can continue upon reconsenting to the randomized withdrawal and final 6-month open-label portion.

All patients will provide consent to enroll into this study. Unless patients have a prior positive amyloid PET scan, MRI showing hippocampal volume loss or other prior evidence of AD, patients will undergo a CSF draw (if all other screening criteria are met) to confirm a total tau/A β_{42} ratio ≥ 0.28 .

Patients will report to the clinic in the morning of Day 1. Prior to dosing, patients will complete the following baseline measures: ECG, vital signs, clinical labs, urinalysis, listen to heart and lungs, ADAS-Cog11, neuropsychiatric inventory (NPI), geriatric depression scale (GDS), and the C-SSRS. A blood sample will be collected for plasma-based biomarkers and genetic testing.

Patients will return to the clinic every month through Month 3 and every 1.5 months through Month 12. Visits on Months 4.5, 7.5 and 10.5 will include vital signs, listening to heart and lungs, AE monitoring, C-SSRS, and drug dispensation and accountability only and may be conducted by telemedicine, based on the judgement of the Investigator. After Month 12, visits will be on Months 13, 15, 18, 21 and 24. Patients completing Month 12 prior to availability of drug supply for the randomized withdrawal phase will continue with active treatment until drug supply is ready and therefore will have an additional "Withdrawal Day 1" visit before resuming with the Month 13 visit one month later.

PK blood samples will be obtained in the morning before dosing at return visits on Months 15 and 18.

Blood draws for clinical laboratory testing and urine collection for urinalysis will be performed at Day 1 and Months 1, 2, 3, 6, 9, 12, 15, 18, 21 and 24. Safety assessments of vital signs and listening to heart and lungs will be conducted at all visits. ECGs will be conducted on Day 1 and Months 1, 3, 6, 9, 12, 18 and 24.

For plasma biomarkers, plasma samples will be collected on Day 1 prior to dosing and on Months 3, 6, 9, 12, 15, 18, 21 and 24. Plasma markers include SavaDx, the complementary diagnostic/biomarker, and a subset of CSF biomarkers (NfL, neurogranin, total tau, $A\beta_{42}$ and YKL40). For the first 50 patients who provided a screening CSF sample, an additional CSF sample will be collected at Month 6 or Month 12 (25 patients each Month 6 and Month 12). This sample will be used to assess CSF biomarker changes. These CSF draws will, however, become OPTIONAL after 50 patients have provided either a Month 6 or Month 12 CSF sample. Further, these optional Month 6 or Month 12 samples should NOT be obtained from patients who did not provide a CSF sample at screening.

An independent Data Safety Monitoring Board (DSMB), will meet periodically to review patient safety assessments and determine if dosing may continue.

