7.2.2. Screening Visit 2 (Days -28 to 0)

This CSF draw is **required for all NEW patients** meeting Screening Visit 1 criteria who do not have a prior positive amyloid PET scan or MRI showing hippocampal volume loss OR prior CSF biomarkers confirming AD. If Screening Visit 2 and Study Day 1 visit are combined, the CSF sample collection will occur 1-3 h after dosing and after the MMSE-2, ADAS-Cog11, NPI and GDS testing has been completed.

- CSF sample collection (5 mL)
- CSF samples should be held at the study site frozen at -70°C, pending shipping instructions from the Sponsor.

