10.3. STATISTICAL ANALYSIS

Biomarker endpoints to be analyzed include: 1) CSF A β_{42} , 2) CSF total tau 3) CSF ptau181, 4) CSF neurofilament light chain, 5) CSF neurogranin, 6) CSF sTREM2, 7) plasma neurofilament light chain, 8) plasma neurogranin, 9) plasma total tau, 10) plasma A β_{42} , 11) SavaDx lymphocyte assay, 12) SavaDx plasma assay and 13) mTOR assay. These data will be analyzed by paired t test comparing baseline to Month 6 or Month 12. Other appropriate statistics may be performed to compare mild versus moderate patients.

The ADAS-Cog11, NPI and GDS endpoints will be analyzed by linear regression with pre-planned comparisons of mild versus moderate patients. Other appropriate statistics may be performed.

Month 12 to Month 18 ADAS-Cog11, NPI and GDS data will be analyzed by mixed model repeated measures (MMRM) analysis. Month 6/12 to Month 18 CSF biomarker data will be analyzed by ANCOVA for the effect of treatment with Month 6/12 value as the covariate, or by ANOVA.

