* Listen to heart and lungs ^a Patients who did not initially consent for a 2-year study should be reconsented at their next study visit.

^b Patients who have a prior amyloid PET or other confirmation of AD can bypass this baseline CSF draw

^c Only for patients with a baseline CSF. Patients with a baseline CSF have the option to do a Month 6 or 12 CSF draw. Month 18 CSF draw is an option only for patients who provided Month 6 or 12 CSF.

^d Include weight for BMI calculation

^e Drug dispensation only at Month 12

NB: Withdrawal Day 1 is only for patients who complete Month 12 prior to drug supply availability for the randomized withdrawal.

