1.3 Study Objectives

The overall study objective is to assess the long-term safety and tolerability of simufilam.

This study has separate sets of objectives for the OL and RW phases. Safety and tolerability are the primary objectives of the OL phase. The primary objective of the RW phase is to assess patient response to blinded, randomized drug withdrawal.

Because drug safety in non-responders can be a critical component of a drug's risk-reward assessment, all patients who completed the 12-month OL phase were eligible to enter the RW phase, regardless of whether they previously showed an apparent response (or not) to open-label drug treatment.

Some study objectives overlap in the OL and RW phases. Hence, objectives are summarized separately below for the OL and RW phases, and for objectives spanning multiple phases. All objectives apply to mild-to-moderate Alzheimer's Disease (AD) patients, 50-85 years of age.

Objectives for the Open-label (OL) phase

- Assess the long-term safety and tolerability of OL treatment with simufilam 100 mg b.i.d. during 12-month repeat-dose oral administration.
- Assess mean changes from baseline on MMSE and compare those changes between patients with mild vs moderate AD.

Objectives for the Randomized Withdrawal (RW) phase

- Assess the safety and tolerability of treatment with simufilam 100 mg b.i.d. versus matching placebo over the 6-months study period.
- Assess patient response to blinded, randomized drug withdrawal on ADAS-Cog11.

Objectives Spanning Overall Study

Exploratory objectives tested across multiple phases are to:

- Characterize the safety and tolerability of simufilam during and up to 24 months of treatment.
- Assess mean changes from baseline on biomarkers and compare those changes between patients with mild vs moderate. For CSF biomarkers, change from baseline to M6 or M12 will be calculated. Plasma biomarkers will be analyzed for change from baseline to M6 and M12 for the OL phase and from M12 to M18 for the RW phase.

Note: All biomarker assessments in this study are exploratory endpoints that are not patient safety related, are 'Research Use Only' products, and, hence, are not intended to be compliant with FDA's Quality System Regulation (QSR) or ISO equivalent.

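### The screening CSF ratio that admits some patients is also their baseline, so open-label change in CSF total tau and Aβ42 carries a regression-to-the-mean bias in the favourable direction, of unknown but probably small size

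*Protocol*

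**What the plan says.** **Gate.** Protocol section 4 sends patients who lack a positive amyloid PET scan, hippocampal volume loss on MRI or other prior evidence of AD to a screening draw: "patients will undergo a CSF draw (if all other screening criteria are met) to confirm a total" tau/Aβ42 ratio of at least 0.28. Protocol 7.2.2 calls this draw "required for all NEW patients" who lack such evidence. Appendix A, footnote b, lets patients with other confirmation bypass it.

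**Same sample as baseline.** Protocol section 4 continues: "For the first 50 patients who provided a screening CSF sample, an additional CSF sample will be collected at Month 6 or Month 12". The group is split evenly between the two visits, and the purpose is stated: "This sample will be used to assess CSF biomarker changes". Appendix A, footnote c, limits follow-up draws: "Only for patients with a baseline CSF". SAP 5.1 defines baseline as the last non-missing value on or before Day 1. No second pre-treatment CSF draw is scheduled, so for CSF this is the screening sample.

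**Analysis.** Protocol 10.3 lists CSF Aβ42 and CSF total tau as its first two biomarker endpoints and says: "These data will be analyzed by paired t test comparing baseline to Month 6 or Month 12". SAP 1.3 says: "For CSF biomarkers, change from baseline to M6 or M12 will be calculated". SAP 5.1 allows, in permissive wording, descriptive statistics for CSF and makes no multiplicity adjustment. SAP 1.1 promises that material deviations from protocol methods are explained in the SAP; none is given for this one. Neither document mentions selection on the baseline value.

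**The concern.** A one-sided cut on a ratio measured with error favours readings in which tau happens to be high and Aβ42 happens to be low. The follow-up reading is not selected, so on average it returns toward the patient's true level. Mean tau then falls and mean Aβ42 tends to rise without any treatment. Protocol 2.3.2 reads that direction as favourable: it takes lower total tau as a sign of less neurodegeneration and describes Aβ42 as low in AD. Months 0 to 12 are open label with no comparator, so nothing in the phase would reveal the artefact. Running all samples in one batch would not remove it, because it comes from selection. A descriptive mean change carries the same bias as a tested one.

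**Working it through.** **Inputs from the documents.** Cut at 0.28, one-sided; 25 + 25 = 50 patients with follow-up CSF; paired t test (Protocol 10.3); two-sided 5% level (SAP 3.2). The plan gives no figure of its own to reproduce.

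**Inputs not in the documents, assumed.** Log-normal markers with between-patient log-SD 0.45 (tau) and 0.40 (Aβ42), true values uncorrelated; within-patient CV (assay plus biological) 8% to 20%, equal for the two analytes; 50% to 85% of those drawn pass; errors independent unless stated.

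**Formula.** Let R = log tau − log Aβ42 at screening, with selection R ≥ c. Let λ = φ(z)/P(pass), where z is the standardised cut. With no drug effect:

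- expected change in log tau = −[Var(e_tau) − Cov] × λ / SD(R)
- expected change in log Aβ42 = +[Var(e_Aβ) − Cov] × λ / SD(R)

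**Worked case: CV 15%, 70% passing, independent errors.**

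- Error variance = ln(1 + 0.15²) = 0.02225
- SD(R) = √(0.45² + 0.40² + 2 × 0.02225) = √0.407 = 0.638
- λ = 0.3477/0.70 = 0.497
- Bias = 0.02225 × 0.497/0.638 = 0.0173, so tau −1.7% and Aβ42 +1.7%

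**Range, with simulated two-sided rejection for tau at n = 50 and no drug effect.**

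| CV | Passing | Tau | Aβ42 | Rejection |
|---|---|---|---|---|
| 8% | 85% | −0.3% | +0.3% | 5% |
| 10% | 85% | −0.4% | +0.4% | about 6% |
| 15% | 85% | −1.0% | +1.0% | about 6% |
| 15% | 70% | −1.7% | +1.7% | 8% to 9% |
| 15% | 50% | −2.7% | +2.8% | about 15% |
| 20% | 50% | −4.6% | +4.8% | about 22% |

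At n = 25, the size at each visit, the last row falls to about 13% to 14%. Without selection the test keeps its level (0.051).

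**Second parameterisation.** With log-SD 0.45 and 0.35, reliability 0.80 to 0.98 and 5% to 40% failing, tau runs from −0.08% to −4.5% and Aβ42 from +0.05% to +2.8%.

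**Correlated errors.** In the worked case, error correlation 0.5 gives 0.01113 × 0.497/0.620 = 0.0089, or about 0.9%. Correlation 0.8 gives 0.00445 × 0.497/0.609 = 0.0036, or about 0.4%. From the formula, the Aβ42 rise vanishes once the correlation reaches SD(e_Aβ)/SD(e_tau). In the second parameterisation that is 0.35/0.45 = 0.78. At correlation 0.8 its worst case is then tau −1.9% and Aβ42 −0.09%.

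**Re-assay.** If half the error variance is assay error and the stored screening sample is assayed afresh for the baseline value, the worked bias halves: 0.0173/2 = 0.0087, or 0.9%.

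**The case against.** The strongest reply is that SAP v3.0 governs the final analysis (SAP 1.2), labels all biomarkers exploratory and points to descriptive statistics for CSF, so the rejection rates describe a test that may never be run. The SAP sentence on within-group significance follows the ANCOVA text for MMSE-2 and does not clearly reach CSF. This stands in part. The exposure under the SAP is mainly a misread mean change, but its wording is permissive and the protocol test has not been withdrawn.

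Second, the size is assumed. That stands: the documents give no CV, reliability or pass rate, and the effect is close to nothing when most patients pass.

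Third, the documents do not say that the eligibility reading is itself the analysed value. CSF is split into two aliquots and frozen (Protocol 7.3.4), and the Phase 2b trial ran screening and Day 28 samples in the same plates (Protocol 2.3.3). A re-assay would remove the assay part of the bias and leave the biological and sampling part.

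Fourth, the gate is not clean. Inclusion criterion 12 asks for evidence of pathology only when MMSE-2 exceeds 26. Protocol 7.2.2 allows a combined Screening Visit 2 and Day 1 with CSF drawn after dosing, in which case the ratio cannot have admitted that patient before the first dose. Patients with prior evidence may skip the draw but are not barred from it. Each of these dilutes the bias, and the number of patients gated is not stated.

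A reader might infer that the gate guarantees a fall in tau and a rise in Aβ42, or that any open-label CSF change is an artefact. The documents support neither. The bias is an expectation of unknown size, and the Aβ42 part can vanish.

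**Conclusion.** The point holds as a bias in expectation. For patients admitted on the screening ratio, open-label mean change is shifted toward lower CSF tau and, unless the errors of the two analytes are strongly correlated, toward higher CSF Aβ42. Under the stated assumptions the shift is roughly 0.3% to 5%, with paired-t rejection of about 5% to 22% at n = 50. It is negligible with a low CV, a high pass rate or shared errors. A change well beyond 5% could not be put down to this mechanism alone on these assumptions. That the mechanism exists follows from the documents; its size rests entirely on inputs they do not give. The gate does not bias the randomized comparison between arms from Month 6/12 to Month 18. The correction is worth making because the bias runs in the favourable direction and the remedy costs almost nothing.

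**What to change.** - **Protocol 10.3:** remove the paired t test of baseline against Month 6 or Month 12 for CSF total tau, CSF Aβ42 and their ratio.
- **SAP 5.1:** replace the permissive wording with a firm statement that these measures are descriptive only in the open-label phase and that no drug-effect conclusion will be drawn from them. Report them with the number of patients who failed the ratio cut, and split by whether entry depended on it. State whether the baseline value is the eligibility reading or a re-assay.
- **Treatment inference:** take it only from the Month 6/12 to Month 18 ANCOVA already in Protocol 10.3, and carry that model into SAP 6.1, which names none for CSF. Say plainly that the Month 18 draw is optional, so the comparison may be small.
- **Reconcile** inclusion criterion 12 and the combined Screening 2/Day 1 visit with the gate in Protocol section 4.

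A truncated-normal correction of the open-label change should not be adopted. In simulation at n = 50 (CV 10% to 20%, 50% to 85% passing) it removed the median bias but had a larger root mean squared error than the raw mean in all nine scenarios, and at 50% passing it was sometimes wildly unstable. It also assumes a single normal population that includes the screen failures.

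The cost is a few lines of wording and one count. The downside is that no open-label significance claim can be made for two exploratory markers.
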